Specific Aim 1: Integrate the My Recovery Plan tool and existing PS tools and strategies to develop a manualized intervention called Recovery Bridge for use by VA PS working to help Veterans make the transition from acute inpatient psychiatric hospitalization to community living.

Specific Aim 2: Complete an open pilot trial (n=15) to examine the feasibility, fidelity, and acceptability of the Recovery Bridge intervention in relation to well specified benchmarks supporting continued and expanded investigation

Specific Aim 3: As part of the open pilot trial: 1) explore the impact of the intervention on readmission rates (at 30 and 90 days), and connection to outpatient care compared to a control group (n of up to 60) identified from administrative data, and; 2) explore the change in recovery and Quality of Life measures over time in the intervention participants.

2 \* Discuss the research design including but not limited to such issues as: probability of group assignment, potential for subject to be randomized to placebo group, use of control subjects, etc.:  
 This is a feasibility and acceptability pilot study and all Veteran participants will receive the intervention; no human subjects control or placebo group will be used.

3 \* Describe the relevant prior experience and gaps in current knowledge. Describe any relevant preliminary data:  
 More knowledge and evidence is needed regarding the use of peer facilitated interventions that support the transition from inpatient mental health hospitalization to living in the community.

As such the overarching purpose of the current study is to optimize existing materials to develop a manualized transitional discharge intervention called Recovery Bridge. The study will also complete an open trial and collect qualitative interview data from a range of stakeholders to examine preliminary outcomes and inform future research to more broadly disseminate and implement the Recovery Bridge Intervention.

4 \* Provide the scientific or scholarly background, rationale, and significance of the research and how it will add to existing knowledge:

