The active sample (n=15) will be compared to a randomly selected contemporaneous (or near-contemporaneous) group-matched sample (n of up to 60) from administrative data on a couple of post-discharge metrics. The first is the SAIL post-discharge engagement metric of 3 outpatient visits within 30 days (or if flagged for suicide risk, 4 outpatient visits within 30 days). The second metric will be whether the patient is re-admitted to in-patient psychiatric hospitalization within 30 days. Matching will be based on diagnostic grouping, age group, and gender. In addition to descriptive statistics (proportions by group), matched pairs analyses (McNemar's test and matched-pairs OR's with 95% confidence intervals) will be used to compare the active sample to the administrative sample on (1) proportion meeting the post-discharge engagement metric, and (2) proportion with inpatient re-hospitalization within 30 days. These analyses are exploratory given limited power and precision of 95% confidence intervals. All quantitative study data will be password protected and stored in a VA REDCap database

Qualitative Analyses: For qualitative data, we will utilize a rapid analysis summary approach. To begin, we will create a summary template with deductively identified key domains (or topics) of interest. We will iteratively refine the summary template by independently summarizing the first few transcripts and then meeting as a team to discuss the summaries, establish agreement, and revise the template with inductively identified domains. When the template is finalized, each of the remaining transcripts will be summarized by an individual and audited by a second person, with disagreements brought to the larger team for discussion. Data from the summaries will be entered into a matrix to begin analysis and identification of common themes. Utilizing this rapid approach will allow us to quickly and efficiently assess the data for the primary outcome of acceptability.

ID: VIEW4E02806052800  
Name: v2\_Sample Size and Data Analysis

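### Connection to outpatient care is compared only as pass/fail at 3 (or 4) visits; adding a visit-count comparison would use information that the cut discards

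*Combined protocol and SAP*

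**What the plan says.** Specific Aim 3 (Justification, Objective, & Research Design) sets out to explore "connection to outpatient care compared to a control group (n of up to 60) identified from administrative data".

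Sample Size and Data Analysis, item 2, is the only place where that outcome is defined. It is a yes/no measure: "The first is the SAIL post-discharge engagement metric of 3 outpatient visits within 30 days". A higher target applies to some Veterans: "or if flagged for suicide risk, 4 outpatient visits within 30 days". The comparison is 15 active Veterans against up to 60 controls: "The active sample (n=15) will be compared to a randomly selected contemporaneous (or near-contemporaneous) group-matched sample (n of up to 60) from administrative data". The planned summary and test are given as "In addition to descriptive statistics (proportions by group), matched pairs analyses", specified as "McNemar's test and matched-pairs OR's with 95% confidence intervals", and the quantity compared is the "proportion meeting the post-discharge engagement metric".

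No mean, median, distribution or rate of visits is planned anywhere. The same section calls these analyses exploratory, with limited power and precision, and says that the pilot is not powered. Control data are described in a companion administrative-data protocol that is not part of the document. For enrolled Veterans, the Prospective Data section lists outpatient encounters scheduled after discharge among the fields collected.

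**The concern.** Connection to care is a matter of degree. Under the plan, a Veteran with 0 visits and one with 2 score the same. So do an unflagged Veteran with 3 visits and one with 6, or a flagged Veteran with 4 and one with 7. Each active Veteran is 1/15 = 6.7 percentage points of the active proportion, so the result can turn on one or two people crossing the line. It can also stay flat although visits have risen.

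With 15 active Veterans there is little precision to spare. The cut should cost most where typical visit numbers lie well away from the threshold, because few Veterans then move across it.

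**Working it through.** **The plan's own figure.** None exists. The documents state no visit rate, effect size or power for this comparison, so there is nothing to reproduce.

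**Inputs.** From the plan: 15 active, up to 60 controls, cut at 3 visits (4 if flagged). Assumed: control mean of 2 to 5 visits in 30 days; counts Poisson, or negative binomial with dispersion k = 2 or 1 (smaller k means more spread); in the simulation, 30% flagged, flag unrelated to visit numbers, and two-sided 5% tests.

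**Step 1: information kept by the cut.** Let p be the probability of reaching the cut t when the mean is μ. The information about μ in the yes/no score is (dp/dμ)² / [p(1−p)]. In the count it is 1/v, where v = μ for Poisson and v = μ + μ²/k for negative binomial. The share kept is the ratio of the two.

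- Poisson, μ = 3, t = 3: p = 1 − e⁻³(1 + 3 + 4.5) = 0.577 and dp/dμ = e⁻³ × 9/2 = 0.224. Share kept = 0.224² / (0.577 × 0.423) × 3 = 0.62.
- Poisson, μ = 5, t = 3: p = 0.875 and dp/dμ = e⁻⁵ × 25/2 = 0.0842. Share kept = 0.0842² / (0.875 × 0.125) × 5 = 0.33.

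Over means 2 to 5 and both cuts, the share kept is 0.33–0.67 (Poisson), 0.41–0.65 (k = 2) and 0.41–0.66 (k = 1). In sample-size terms, 15 × 0.33 ≈ 5 and 15 × 0.67 ≈ 10, so 15 Veterans carry about the information of 5 to 10.

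**Step 2: power, 15 v 60, rate ratio 1.5** (1,500 simulated trials per scenario; score test on pass/fail v Mann-Whitney on counts).

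| Control mean | Poisson | k = 2 | k = 1 |
|---|---|---|---|
| 2 | 45% v 57% | 25% v 29% | 18% v 18% |
| 3 | 49% v 73% | 23% v 30% | 17% v 21% |
| 4 | 34% v 83% | 18% v 33% | 15% v 20% |

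With no effect, the error rates were 3.9–6.1% (pass/fail) and 4.0–5.8% (counts).

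**Step 3: power with 15 one-to-one pairs**, closer to the planned McNemar test. Over control means 2 to 4, exact McNemar gave 10–18% (Poisson) and 5–7% (k = 2 or 1). Signed-rank on counts gave 38–58% and 12–20%. Exact McNemar needs at least 6 discordant pairs, all in one direction (2 × 0.5⁶ = 0.031; 5 pairs give 0.0625). Part of this gap is the conservatism of the exact test, whose error rate under no effect was only 0.9–1.7%. It should not all be charged to the cut.

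**Step 4: sensitivity to the effect size** (3,000 simulated trials per scenario, 15 v 60, single cut at 3; chi-squared v rank test).

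- Ratio 1.6, k from 1.5 to 3: control mean 2, 27–36% v 30–42%; mean 4, 18–23% v 34–54%.
- Ratio 1.6, k = 1: mean 2, 21% v 22%; mean 4, 14% v 25%.
- Ratio 1.3, k from 1 to 3: mean 2, 11–16% v 11–16%; mean 4, 8–11% v 11–22%.

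The gain is therefore close to nil at a mean of 2 with a small effect or strong overdispersion. It grows as the mean rises above the cut.

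**Step 5: does the count method hold its error rate?** Under no effect at 15 v 60 (k from 1 to 3), Poisson regression with an uncorrected sandwich standard error rejected in 6.8–8.4% of trials, and in up to 10% once assumed matching covariates were added. Negative-binomial Wald tests gave 5–6%. The choice of count method matters at this size.

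**The case against.** The strongest reply is that nothing here is wrong. The SAIL measure is a named service metric, the comparison is declared exploratory and unpowered, and the main purpose of the pilot is feasibility, fidelity and acceptability. More visits may also reflect greater need rather than better connection, and with 15 Veterans a few heavy users can drive a mean ratio. All of this stands as a reason to keep the SAIL proportion and treat counts as supporting. It is not a reason to leave counts out, since limited precision argues for using the information to hand.

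A reader might go further than the documents allow in four ways.

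- That counts should replace the metric or become the main comparison. Nothing in the documents makes the metric unsuitable for its stated exploratory use.
- That the power gain is assured. Every visit mean, dispersion and ratio above is assumed, and under some of them there is no gain.
- That counts are already in hand for both groups. For up to 60 controls this depends on the companion protocol, which might supply only a ready-made indicator. For enrolled Veterans, the listed field refers to scheduled encounters, which need not be attended visits.
- That this is the one services outcome with enough events to be informative. The documents give no rate for this metric or for 30-day readmission.

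**Conclusion.** The point holds as a modest improvement to the analysis. The plan compares connection to outpatient care only as a proportion above a cut, although scoring the cut requires the count. For means of 2 to 5 visits, Poisson to k = 1, the cut keeps about 33–67% of the information. In the scenarios tabulated for 15 v 60 at a rate ratio of 1.5, the rank test on counts matched or beat pass/fail, by 0 to 5 points at k = 1 and by up to 49 points (34% v 83%) for Poisson counts with control mean 4. Both versions stay underpowered in most overdispersed scenarios, so the benefit is a fuller and somewhat more precise description, not a decisive test. The size rests wholly on the assumed visit distributions; the gap in the plan does not.

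**What to change.** Keep the SAIL proportion as the planned comparison. Before the data are analysed, add a supporting exploratory comparison of the number of attended outpatient visits in 30 days:

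- Report the median and range by group.
- Give a between-group estimate with a 95% confidence interval from a method that holds its error rate with 15 Veterans. Examples are a rank-based shift, or a negative-binomial rate ratio with small-sample or permutation inference. Do not use Poisson regression with an uncorrected sandwich standard error.
- Account for the matching variables (diagnostic grouping, age group, gender) and for suicide-risk flag status, which sets the visit target.
- Apply one counting rule to both groups, based on attended visits, with Recovery Bridge study sessions not counted as outpatient visits. Only active Veterans receive these sessions. With about five planned and the first on the inpatient unit, 5 − 1 = 4 could follow discharge. If counted and held within 30 days, those alone would meet either target. This rule is needed for the SAIL proportion as well.
- Confirm that the companion administrative-data protocol pulls visit-level counts for controls, not only a pass/fail indicator.

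The cost is some extra analysis and one more exploratory estimate, on a scale other than the SAIL benchmark. No new participants or study visits are needed. If the companion protocol does not already pull counts, its data request would have to be extended.

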## Study Procedures

**If you uploaded a separate research protocol document in the 'Research Protocol' page, cite the applicable section and page numbers from that document in the answer boxes below. (If this study is a collaborative UM/VA study please list each procedure that is being conducted and the locations where it is being conducted.)**

- 1 \* Describe all procedures being performed for research purposes only (these procedures would not be done if individuals were not in the study) and when they are performed, including procedures being performed to monitor subjects for safety or to minimize risks:

15 (N=15) Veterans, who are slated for discharge from the VAMHCS inpatient psychiatric unit, will participate in a pilot study to examine the feasibility and acceptability of Recovery Bridge (a web-based tool) as a transitional discharge intervention designed to decrease inpatient re-admission rates and improve Veteran's hope, recovery orientation, and quality of life. Our research staff will monitor the census of the inpatient unit every day and recruit Veterans as early as possible during their stay. Study staff will approach Veterans to explain the study and allow ample time for questions and evaluation of capacity to provide consent. Those consented will be asked to complete a brief (30-45 min) quantitative, baseline assessment. The two PS working on the project will also be available to meet the Veteran at the hospital during the recruitment and assessment process to help establish and build rapport. The consent meeting and the baseline assessment will be done in person on the inpatient unit. They will be conducted in a private and confidential space.

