All enrolled Veterans will participate in the Recovery Bridge intervention which will take place over approximately five, 30-75 minute sessions. The first session will take place in-person on the inpatient unit (with the peer specialist using a government issued laptop to access the web-based program) in a private and confidential space. The remaining sessions will occur either in person, over the VA approved video platform, Microsoft Teams, or over the phone, at the participants' convenience. The web-based Recovery Bridge intervention will include instructions on how to tailor and apply myriad Peer Specialist skills and strategies to the context of working with Veterans transitioning from inpatient psychiatric hospitalization to community living. It will also include tailored instructions for using the tools modules relating to: 1) Daily wellness; 2) managing triggers and early warning signs, and; 3) what to do when things breakdown (including crisis and safety plans developed in concert with licensed independent providers). Veterans will be able to access the intervention with assistance from the peer specialist who will have a government issued laptop. Sessions may be audio or video recorded for fidelity purposes.

Veteran Participants:

Approximately 7 days following the final intervention session, all Veteran participants will complete a 30-45 minute quantitative, post-assessment along with a 30-60 minute qualitative interview regardless of the number of intervention sessions attended in order to understand barriers and facilitators to engaging in the intervention. This final assessment along with the qualitative interview will be done over the phone or via VA approved Video platform, Microsoft Teams.

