#### All Participants:

All qualitative interviews will be conducted by video meeting, or phone and audio-recorded following IRB/ORD approved informed consent procedures via Microsoft Teams. For the Veterans enrolled in the study, the qualitative guidelines will have already been discussed and agreed to during the informed consent process. For the stakeholders and Peer Specialists who will be interviewed, they will be provided an information sheet relaying all the information of the portion of the study they will take part. They will read and discuss with study staff before agreeing to the interview. Recordings of all interviews will be transcribed verbatim by a VA & IRB approved service (Microsoft Teams) then proofread against the recording (and anonymized in the process) by members of the study team.

An administrative data only control sample will be established to pull matched services data for up to an additional 60 Veterans

2 \* **Describe all procedures already being performed for diagnostic or treatment purposes (if not applicable to the study, enter "N/A"):**  
N/A

3 \* **Describe the duration of an individual participant's participation in the study:**  
Veteran subjects participation will last approximately two months. Peer Support Specialist and interventionist and stakeholder participation (as human subjects to complete a single qualitative interview) will last 30-60 minutes each.

4 \* **Describe the amount of time it will take to complete the entire study:**  
The entire study will be completed within 18 months.

5 \* **Describe any additional participant requirements:**  
N/A

ID: VIEW4E0280585B400  
Name: v2\_Study Procedures

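### Exploratory engagement comparison: the suicide-risk flag sets each patient's visit threshold but is not a matching variable, so a different flag mix can shift the result by a few points

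*Combined protocol and SAP*

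**What the plan says.** Specific Aim 3 (Justification, Objective, & Research Design, item 1) explores readmission and "connection to outpatient care compared to a control group (n of up to 60) identified from administrative data". Sample Size and Data Analysis, item 2, makes the engagement outcome the SAIL post-discharge metric: 3 outpatient visits within 30 days, "or if flagged for suicide risk, 4 outpatient visits within 30 days". On choosing controls it says "Matching will be based on diagnostic grouping, age group, and gender". The two groups are then compared by McNemar's test and matched-pairs odds ratios. No stratification or adjustment by flag is stated. The plan's own caveat is "These analyses are exploratory given limited power and precision of 95% confidence intervals", and item 1 of the same section says the pilot is not powered.

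On the intervention, Study Procedures, item 1, plans about five sessions. "The first session will take place in-person on the inpatient unit"; "The remaining sessions will occur either in person", by video or by phone. Item 3 puts Veteran participation at about two months. The administrative data are described in companion protocol HP-00110495, which is not among the documents supplied.

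**The concern.** The flag decides how many visits a patient needs, so two Veterans with identical visits can be scored differently because one is flagged. If the active group holds a larger share of flagged Veterans than the controls, its proportion engaged is pulled down with no difference in care; if a smaller share, it is pulled up. The mix need not agree. Under Recruitment, item 1, active participants are volunteers approached after unit staff have raised the study and the treatment team has been consulted, whereas controls are drawn at random from records. Matching on diagnosis, age and gender may balance the flag in part, but nothing ensures it.

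A second question arises from the same outcome. Only the active group has study Peer Specialist sessions after discharge. If those contacts count as outpatient visits, delivering the intervention goes some way towards meeting the outcome. That would be a one-directional effect, and a caveat about power and precision does not describe it.

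At stake is how one exploratory contrast is read.

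**Working it through.** The plan states no event rate, effect size or power for this comparison, so there is no figure of its own to reproduce. Visit rates and flag shares below are assumptions.

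**Inputs from the documents.** Thresholds of 3 and 4 visits in 30 days; 15 active and up to 60 controls; about five sessions with the first on the inpatient unit, so up to about 5 − 1 = 4 after discharge.

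**Assumptions.** Visits in 30 days are Poisson and 60% of patients reach 3. The mean is then 3.105, with P(≥3) = 0.600 and P(≥4) = 0.376, a gap of 0.224.

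**1. Shift from a flag imbalance.** With flag share f, the proportion engaged is (1 − f) × 0.600 + f × 0.376. The between-group difference is therefore (difference in flag share) × 0.224, lower for the group with more flagged patients.

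- Flag shares of 50% and 20%: 0.30 × 0.224 = 0.067, about 7 points.
- Same imbalance with 50% or 75% of patients reaching 3: 0.066 or 0.060.
- Same imbalance with over-dispersed visits (negative binomial, variance 1.5, 2 or 3 times the mean): 0.055, 0.048 or 0.039.

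**2. If flagged Veterans make more visits.** The lines above give both groups the same visit rate.

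- 20% more visits: P(≥4) = 0.511, and the shift is 0.30 × (0.600 − 0.511) = 0.027.
- About 34% more visits: the shift is zero. Beyond that it changes sign.

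**3. Imbalance expected by chance.** The SD of the difference in flag share is √[p(1 − p)(1/15 + 1/60)]: 0.115 at p = 0.20 and 0.144 at p = 0.50. Multiplied by 0.224, this gives 0.026 and 0.032, about 3 points.

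**4. Yardstick.** The unpaired standard error of the difference in proportions at 60% engaged is √(0.24/15 + 0.24/60) = 0.141, about 14 points. Every shift above is smaller.

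**5. After matching on the flag.** Both members of a matched set face the same threshold. The flag-share difference is zero within sets, and so is the shift.

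**6. Secondary point, only if study sessions count.** With k sessions counted within 30 days for every Veteran and routine visits unchanged, the proportion engaged is P(≥3 − k) if unflagged and P(≥4 − k) if flagged.

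| k counted | 0 | 1 | 2 | 3 | 4 |
|---|---|---|---|---|---|
| Unflagged | 0.600 | 0.816 | 0.955 | 1.000 | 1.000 |
| Flagged | 0.376 | 0.600 | 0.816 | 0.955 | 1.000 |

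The k = 0 column is fully consistent with the text. The k = 3 and 4 columns are extremes: session spacing is not stated, and participation of about two months suggests that some sessions fall after day 30. With over-dispersed visits, k = 1 gives 0.75 to 0.79 for unflagged Veterans.

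Excluding study sessions can err the other way. If one counted session displaces half a routine visit on average, the mean falls to 3.105 − 0.5 = 2.605. The count including the session gives P(≥2) = 0.734, the count excluding it gives P(≥3) = 0.483, and the figure without intervention is 0.600. The two counts fall on either side of it, so both would be needed.

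**The case against.** **The flag is already in the outcome.** Each patient is held to the threshold for his or her own flag status, so leaving the flag out of the matching is a design choice. If flagged Veterans make about a third more visits, in line with the extra visit asked of them, the shift disappears. The 50% versus 20% imbalance has no source in the documents. All of this stands, and it rules out a reading that a reader might infer: that the comparison is wrongly specified or biased in a known direction. What remains is that the mix can differ, that its effect is then mixed with any real difference, and that the flag has to be obtained anyway to score the metric.

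**Reporting the flag by group would be enough.** Reporting shows an imbalance but does not remove it. Matching removes it. A fourth variable does thin the cells, and that cost is real, but the control number is an upper limit.

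**The intervention meeting its own outcome is conjecture.** A reader might infer that the sessions inflate engagement. The documents do not show this. Study Procedures lists the sessions under research-only procedures in item 1 and answers N/A for existing diagnostic or treatment procedures in item 2, which leans against their being recorded as care encounters. The SAIL definition and HP-00110495 may settle what counts, and neither was supplied. The answer on medical-record entry (Confidentiality of Data, item 5) cannot be read in the extracted text, and that is no fault of the plan. The objection stands: this part is conditional.

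**The comparison is exploratory and unpowered.** Agreed, and the severity is set accordingly.

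**Conclusion.** The point holds as a small, inexpensive improvement to an exploratory analysis. The outcome threshold depends on a variable that the matching ignores, so the proportion engaged can shift in either direction for reasons unrelated to care. Under the assumed visit rates the shift is about 0 to 7 points for a 50% versus 20% imbalance, and about 3 points for a one-SD chance imbalance. Both are below the standard error of about 14 points. It reverses if flagged Veterans make more than about 34% more visits. These sizes rest on assumed Poisson or over-dispersed visits and assumed flag shares; the chance calculation also ignores any balance gained from the existing matching variables.

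The session-counting question is secondary. It has no effect if study sessions do not count. If they do, it could be larger than the flag effect and would favour the active group.

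Confidence is medium, because the metric's definition and the companion protocol were not available. The feasibility and acceptability conclusions are untouched.

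**What to change.** In Sample Size and Data Analysis, item 2:

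1. Add suicide-risk flag (yes/no) to the matching variables. Where a cell holds few controls, accept fewer; a sample of up to 60 permits this. Report flag status by group.
2. Keep the SAIL metric as planned. If study Peer Specialist sessions count as outpatient visits under SAIL and HP-00110495, report alongside it the same comparison with those sessions excluded, identified from the study's own session dates. Note that this count may understate engagement if sessions displace routine visits. If they do not count, no change is needed.
3. Keep the wording consistent with HP-00110495.

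The cost is one matching variable that scoring already requires (the field list under Prospective Data, item 2, does not name it, though HP-00110495 may), slightly fewer eligible controls per cell, and one extra exploratory analysis only if sessions count. In that case the second figure may be less favourable to the active group.
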